8.3.3. Major Analysis Protocol Deviations

The following protocol deviations are considered as major and as having an impact on analyses of efficacy data:

- [REDACTED]
- [REDACTED]
- [REDACTED]

Additional categories may be specified in the applicable SAP. Numbers of subjects with deviations in each category will be provided by both randomized and actual treatment.

8.4. General Analyses

8.4.1. Demographics and Other Baseline Characteristics

Demographics and baseline characteristics including age, sex, race, ethnicity, creatinine clearance, weight, BMI, UC characteristics, previous and current UC medications by category, and other medical history will be summarized. For subjects enrolled in the Maintenance Study, baseline characteristics at both the time of entry into the Induction Study and the time of entry into the Maintenance Study will be summarized.

8.5. Analysis of Efficacy

8.5.1. Phase 2b Induction Efficacy Endpoints

Refer to [DEFINITION OF TERMS](#)

- [REDACTED]
- [REDACTED]
- [REDACTED]
- [REDACTED]

8.5.4. Primary Efficacy Evaluation

For efficacy evaluations, the null hypothesis for treatment comparisons will be that there is no difference between a given dose level of TD-1473 and placebo; the alternative hypothesis will be that there is a difference.

For primary endpoints of each study, missing data and sensitivity analyses will be performed. Further details will be given in each applicable SAP.

Phase 2b Induction:

The primary endpoint is reduction in total Mayo score at Week 8. An analysis of covariance (ANCOVA) model will be used with terms for the stratification factors, baseline score, and treatments, and each TD-1473 dose will be compared to placebo. Missing Week 8 scores will not be imputed.

Phase 3 Induction:

The primary endpoint is clinical remission at Week 8. Each active dose selected will be compared to placebo using a stratified Cochran-Mantel-Haenszel (CMH) test, stratifying by randomization stratum. Subjects with missing data or who meet a treatment failure criterion will be counted as not meeting the endpoint of clinical remission (Refer to Section 8.9).

Phase 3 Maintenance:

The primary endpoint is clinical remission at Maintenance Week 44. Each active dose selected for continued evaluation in the Maintenance Study will be compared to placebo using a stratified CMH test, stratifying by randomization stratum. Subjects with missing data or who meet a treatment failure criterion will be counted as not meeting the endpoint of clinical remission (Refer to Section 8.9).

8.5.5. Secondary and Additional Efficacy Evaluations

Unless otherwise specified, binary endpoints will be analyzed using stratified CMH tests, stratifying by randomization stratum, similar to the primary efficacy endpoint. As appropriate, subjects with missing data or who meet a treatment failure criterion will be counted as not meeting the endpoint. Criterion of treatment failure for each endpoint will be described in the SAP. Selected binary endpoints will also be analyzed by fitting logistic regression models and choosing a dose-response model by a method specified in the applicable SAP. Confidence intervals (95%) for treatment differences will be provided.

Quantitative and score efficacy endpoints collected at a single scheduled time point postbaseline will be analyzed by fitting ANCOVA models including terms for treatment effects and stratification factors. The baseline value of each endpoint (or transformed endpoint if a

transformation is specified) will be included as a covariate. For score endpoints, adequacy of the fitted ANCOVA/MMRM models will be assessed and models for ordinal categorical data may be fitted as sensitivity analyses.

Quantitative efficacy endpoints with multiple scheduled postbaseline assessments ([REDACTED]) will be analyzed by fitting mixed effects repeated measures models (MMRM). SAS procedure MIXED will be used to fit models with random subject effects, an unstructured covariance matrix, and including terms for stratification factors, visit, and baseline score by visit and treatment by visit interactions. [REDACTED]

For the Phase 2b and Phase 3 Induction studies, the primary assessment for all primary and secondary endpoints will be at Week 8; results from subjects who do not demonstrate clinical response at Week 8 and receive additional study treatment during the Extended Induction period will be summarized descriptively.

8.5.6. Multiplicity Adjustment

Within each study, hypothesis testing will be conducted with a gatekeeping approach to control the overall family-wise type 1 error rate at 5% (2-sided). How this will be achieved including the organization of hypothesis families will be described in the Statistical Analysis Plan (SAP). In general, if there are multiple hypotheses within a family, at least 1 hypothesis must be rejected in order for testing to proceed to later families. Logic gates will also be applied in that if a dose group does not pass an endpoint, this dose group will not be tested in subsequent families.

In addition, nominal p-values will be reported for all efficacy endpoints, including the additional efficacy endpoints.

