8.2.1. Induction Phase 2b Sample Size Considerations

A sample size of 60 subjects per group was estimated to give approximately 90% (89%) power to detect a 2-point active dose group vs. placebo improvement in total Mayo score at all three doses, given the following:

- Hochberg step-up procedure adjustment for multiple comparisons, with family-wise type 1 error rate to be controlled at 5% (2-sided tests)
- Residual change SD of 3 points

The estimated power to detect a 2-point improvement relative to placebo for at least one of the three doses was greater than 98%.

Assuming a slightly higher residual change SD of 3.5 points, the estimated power to detect a 2-point active dose group vs. placebo improvement in total Mayo score at all three doses was approximately 73% and the estimated power to detect a 2-point improvement at one or more of the doses was approximately 94%. Estimates were obtained using East software, with 10,000 simulations per case.

Subjects will be stratified by prior biologics failure and baseline corticosteroids use at randomization. In addition, randomization caps will be placed on both prior biologics failure subgroups [no to biologics failure (60%) and yes to biologics failure (60%)] to ensure that neither subgroup is overrepresented.

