1. INTRODUCTION

This document outlines the plan for the summarization and analysis of clinical data collected in the Phase 2b Induction Study of Protocol 0157 for TD-1473.

Protocol 0157 comprises 3 separate studies within a single protocol. The purpose of multiple studies within a single protocol is to increase operational efficiency and reduce operational costs.

The analyses and summarization of clinical data is divided into 3 separate SAPs corresponding to the separate studies within the protocol:

- Phase 2b Dose-Finding Induction SAP (this document)
- Phase 3 Dose-Confirming Induction SAP
- Phase 3 Maintenance SAP

Each study set of analyses will control Type I error < 0.05 . As such, study analyses (Phase 2b Induction Study, Phase 3 Induction Study, Phase 3 Maintenance Study) are considered independent and no control of multiplicity will occur across the 3 sets of analyses.

The analysis of pharmacokinetics data (derivation and summarization of individual PK parameters) is outside the scope of this document and is not addressed here.

This document describes the a priori plan for analysis. Any substantive modification to this analysis plan will be identified in the clinical study report (CSR).

Information in the appendices to the SAP are not considered a formal section of the signed SAP.

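### Does letting one rejected dose open the next family break the 5% family-wise error control?

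*Protocol*

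**What the plan says.** Protocol 8.5.6 (Multiplicity Adjustment) promises, within each study, a gatekeeping approach to "control the overall family-wise type 1 error rate at 5% (2-sided"). It then hands over the details: "How this will be achieved including the organization of hypothesis families will be described in the Statistical Analysis Plan (SAP"). Two features are sketched. The first is introduced as a general rule: "at least 1 hypothesis must be rejected in order for testing to proceed to later families". The second is a dose-wise gate: "if a dose group does not pass an endpoint, this dose group will not be tested in subsequent families". No level is given for any family after the first.

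Hochberg is named in the sample-size text (protocol synopsis and 8.2.1 to 8.2.3; section 1.5 of both SAPs). In protocol 8.2.1 the power assumption reads "Hochberg step-up procedure adjustment for multiple comparisons, with family-wise type 1 error rate to be controlled at 5% (2-sided tests"). The Phase 2b SAP, section 1, repeats the commitment: "Each study set of analyses will control Type I error" below 0.05. Its sections 3.3.3 and 3.4.2 say that a multiplicity procedure is planned for the primary and the key secondary endpoint. Its contents list that procedure as section 3.5, but the text of that section is not in the public copy.

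The Phase 2b hierarchy has two families of three dose comparisons: change in total Mayo score, then clinical remission at Week 8.

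**The concern.** Ordinary Hochberg has no alpha left over unless every hypothesis in the family is rejected. Suppose one dose works on the primary endpoint and another does nothing. The full 5% is then at risk on the inactive dose, and the active dose goes on to the remission test. Any positive level used there pushes the total above 5%. The dose-wise gate does not help, because the dose that passed is exactly the one tested next.

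Read together, the Hochberg assumption and the one-rejection rule seem to describe this procedure. If they did, the 5% claim for the primary and key secondary endpoints would fail, in a study whose remission result feeds dose selection (protocol 8.11). The unreadable SAP section could be set aside only if the stated powers proved that full-5% Hochberg was in use. In that case either the error claim or the power claim would have to be wrong.

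**Working it through.** **Inputs.** From protocol 8.2.1: 60 per arm, 2-point difference, SD 3 (alternative 3.5), 5% two-sided, 10,000 simulations per case. From 3.1: three doses and placebo, 1:1:1:1. The correlation between the two endpoints is not given, so it was varied from 0 to 0.9.

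**1. The plan's own power.** The protocol states: "A sample size of 60 subjects per group was estimated to give approximately 90% (89%) power" for all three doses. At SD 3 each comparison has an expected statistic of 2 / (3 × √(2/60)) = 2 / 0.5477 = 3.65. Simulating ordinary Hochberg with a shared placebo arm gives 88.9% for all three doses and 98.4% for at least one. At SD 3.5 it gives 73.9% and 93.8%. The stated figures are reproduced.

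**2. The error if both families got a full 5%.** Upper bound: 5% + 5% = 10%. If the two families were independent: 1 − 0.95² = 9.75%. Simulated for three doses with the dose-wise gate applied and no true effect on remission:

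| Truth on the primary endpoint | Correlation 0 | 0.5 | 0.9 |
|---|---|---|---|
| One or two doses very effective, the rest null | 9.6% | 9.4% | 8.9–9.0% |
| One or two doses at the planned effect, the rest null | 8.8–9.0% | about 8.1% | 6.6–6.8% |
| No dose effective | 4.6% | 4.6% | 4.6% |

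So the arithmetic behind the worry is right, on the condition that the second family is tested at a full 5% after a partial rejection.

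**3. A procedure that fits every readable sentence and keeps 5%.** Truncated Hochberg with fraction γ compares the i-th smallest of n p-values with [γ/(n − i + 1) + (1 − γ)/n] × 5%. If m ≥ 1 hypotheses remain unrejected, it passes on (1 − γ)(1 − m/n) × 5%. If all are rejected, it passes on 5%. Testing continues after one rejection, and the dose-wise gate can be applied. With γ = 0.95 and one effective dose, the simulated family-wise error is at or below 4.8%.

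**4. Can the stated powers tell the two apart?**

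| γ | All three, SD 3 | At least one, SD 3 | All three, SD 3.5 | At least one, SD 3.5 |
|---|---|---|---|---|
| Stated | 89% | above 98% | 73% | 94% |
| 1 (ordinary) | 88.9% | 98.4% | 73.9% | 93.8% |
| 0.95 | 88.6% | 98.4% | 73.4% | 93.8% |
| 0.8 | 87.5% | 98.3% | 71.7% | 93.7% |
| 0.5 | 84.9% | 98.2% | 67.4% | 93.4% |

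The simulation error of the stated figures is √(0.89 × 0.11 / 10,000) = 0.3 points at SD 3 and √(0.73 × 0.27 / 10,000) = 0.4 points at SD 3.5. The row for γ = 0.95 rounds to the stated values in every column. Ordinary Hochberg rounds to 74% rather than 73% in one of them. The powers rule out γ = 0.5, but they do not rule out truncation.

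**5. Is a false remission claim nearly twice as likely?** No. The 9% to 10% is the chance of a false total Mayo claim or a false remission claim or both. Under the full-5%-twice assumption with one effective dose, and correlations from 0 to 0.7, the chance of a false remission claim alone is 5.0% to 5.9% when that dose is very effective and 4.4% to 4.5% at the planned effect.

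**6. Which studies could be affected?** The Maintenance SAP, section 3.5, drops hypothesis testing and multiplicity adjustment because the study ended early. Protocol 3.1 plans a single dose for Phase 3 Induction, so a partial rejection within a family cannot occur there. That leaves Phase 2b.

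**The case for a change.** The strongest reply is that the powers still limit how much truncation is possible. With γ = 0.95, the level left for remission is (1 − 0.95)(1 − 2/3) × 5% = 0.08% after one rejection and (1 − 0.95)(1 − 1/3) × 5% = 0.17% after two. With γ = 0.9 it is 0.17% and 0.33%. A key secondary tested at such levels has little chance of success, and no readable passage states the level. So, the reply goes, either control fails, or the power is overstated, or remission is close to untestable after a partial rejection.

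The calculation stands, but it does not show an error. The third branch costs power on the key secondary, and the protocol claims no power for remission in Phase 2b. When all three doses pass, which is the case the study is powered for, the full 5% moves on. It is also true that 8.5.6 alone would not stop a careless reader from using 5% twice. But that section names the SAP as the place where the method is set out, and a withheld section cannot be counted as an omission. The two-dose contingency for Phase 3 Induction in protocol 8.2.2 is in the same position, since the Phase 2b SAP (section 1) assigns that study a SAP of its own.

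**Conclusion.** The concern does not hold. The conditional result is correct: 5% spent twice after a partial rejection gives a family-wise error of about 9% to 10% at worst, and about 6.6% to 9.0% at the planned effect. Nothing readable says the plan does this. The governing section commits to 5%, states its gate only in general terms, names no level for the second family, and defers the method to a section that cannot be read here. The attempt to infer the method from the powers fails, because a mildly truncated Hochberg matches all four stated figures and keeps the error within 5%. The conclusion rests on simulations with a shared placebo arm and assumed endpoint correlations of 0 to 0.9, and on not treating the withheld SAP text as missing from the plan. What is left is a detail to look up in the full SAP, with Phase 2b as the only study concerned.

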8.6. Analysis of Pharmacokinetics

For all PK data analyses, the PK analysis set will be used. PK analyses will follow the PK SAP; additional analyses may also be conducted as appropriate.

Appropriate PK parameters and/or mathematical modeling results for TD-1473 will be listed and summarized using descriptive statistics by dose group, as appropriate.

Estimates of PK parameters will be calculated using a population PK approach; data may be pooled across studies to better inform the model. Population PK results will be presented in a separate report. Pertinent subject information such as actual dosing times and PK sampling times and concomitant medications will be recorded to enable PK parameter estimation in a population PK analysis. Plasma samples from selected subjects may be used for additional profiling studies with data summarized in a report separate from the CSR.

8.7. Analysis of Pharmacodynamics

Whole blood and serum samples will be collected as described in the Schedule of Study Procedures tables (Table 1 and Table 2). PD analyses (including PK exposure vs. response analyses for efficacy, safety and/or biomarkers) will be detailed as appropriate in a report separate from the CSR. Samples from selected subjects may be used for potential future exploratory biomarker profiling and reported elsewhere.

8.8. Safety Analyses

Safety summaries for the Phase 2b Induction, Phase 3 Induction, and Phase 3 Maintenance studies will include all subjects who received at least one dose of study drug. This will include subjects who are randomized to TD-1473 doses not selected for continued evaluation in the Phase 3 studies.

Summaries will be provided by scheduled visit and time point or for the entire treatment period, as appropriate. Quantitative data collected at unscheduled times will be listed but will not be included in summaries. Categorical data collected at unscheduled times (e.g., ECG finding categories) will not be included in summaries by time point but will be included in summaries of findings during the entire treatment period.

Safety variables to be summarized include vital signs, adverse events, clinical laboratory results (hematology, chemistry, and urinalysis), and corrected QT interval (QTcF).

For the Phase 2b and Phase 3 Induction studies, the primary assessment period for all safety endpoints will be the first 8 weeks.

8.8.1. Extent of Exposure

Extent of exposure will be calculated from data collected in the study drug administration page of the CRF and summarized. Reasons for study drug discontinuation will be summarized. For each subject, treatment compliance over the interval from first to last dose will be calculated from data collected in the study drug administration and drug accountability pages of the eCRF. Treatment compliance will be summarized by actual treatment received.

8.8.2. Adverse Event Data

AEs will be coded to the preferred terms of the Medical Dictionary for Regulatory Activities (MedDRA®). Summaries will present by system organ class (SOC), preferred term (PT), and severity (mild, moderate, severe), the number and percentage of subjects reporting each AE.

A Treatment Emergent Adverse Event (TEAE) will be defined as any AE that begins on or after the date of the first dose of study drug.

The number and percentage of subjects who reported TEAEs will be summarized as follows:

- All TEAEs, by SOC and PT and also by PT (by descending overall frequency)
- All TEAEs of Special Interest (Section 7.1.4) by SOC and PT.
- All TEAEs, by SOC, PT, and severity
- All study drug-related TEAEs, by SOC and PT
- All study drug-related TEAEs, by SOC, PT, and severity
- All TEAEs leading to premature discontinuation of study drug, by SOC and PT
- All TEAEs leading to temporary interruption of study drug, by SOC and PT
- All TESAEs, by SOC and PT
- All study drug-related TESAEs, by SOC and PT

A listing will be provided for all subjects who experience an SAE. Listings will also be provided for subjects who discontinued study treatment prematurely because of AEs and subjects who temporarily interrupted study treatment because of AEs. AESIs (Section 7.1.4) will also be listed.

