6.4.1.3. Medical History

A medical history will be taken during screening and will include evaluation for past and present cardiovascular, respiratory, GI, renal, hepatic, neurological, endocrine, lymphatic, hematologic, immunologic, dermatologic, psychiatric, genitourinary diseases, surgical history, or any other diseases or disorders. An updated medical history will be obtained on Day 1 prior to dosing. Medical events or conditions that arise or worsen in severity or frequency following informed consent will be recorded as an AE; those after initiation of Study drug will be recorded as a treatment-emergent AE.

Regarding the subject's history of UC, the years since diagnosis and extent of disease (categorized as proctosigmoiditis, left sided, extensive or pancolitis) should be documented. The number of stools per day (rounded to the nearest whole digit) when the subject was feeling normal (without a flare or before the diagnosis of UC) should be recorded. This will be used to calculate the stool frequency subscore.

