7.1.1. Adverse Events (AE)

An AE is any untoward medical occurrence in a patient or clinical trial subject administered a pharmaceutical product that does not necessarily have to have a causal relationship with this treatment. An AE can therefore be any unfavorable and unintended sign (including an abnormal laboratory finding), symptom, or disease temporally associated with the use of a medicinal product, whether or not related to the medicinal product.

- AEs may be new events
- Preexisting events that increase in frequency, severity or change in nature or seriousness during or as a consequence of participation in clinical studies.
- Pre- or post-treatment complications that occur as a result of a protocol-mandated procedure (such as a biopsy).
- AEs may be clinically significant changes from baseline in physical examination, laboratory tests, or other diagnostic investigation (e.g., laboratory results, x-ray findings).
- AEs may result from an overdose of the Study medication.

Whenever possible, the diagnosis (rather than a series of terms related to a diagnosis) should be recorded as the AE term.

An AE does not include the following:

- Medical or surgical procedures (such as surgery, endoscopy, tooth extraction, or transfusion); the condition that leads to the procedure is an adverse event
- Preexisting diseases or conditions present or detected before signing an informed consent form that do not worsen
- Situations where an untoward medical occurrence has not occurred (such as hospitalization for elective surgery or social and/or convenience admissions)
- Overdose of either Study drug or concomitant medication without any signs or symptoms, unless the subject is hospitalized for observation

Any medical condition or clinically significant laboratory abnormality with an onset date prior to the time the subject signed the informed consent form is considered to be preexisting and should be documented in the medical history CRF.

Pregnancy is not an AE; however, if a female subject becomes pregnant during the conduct of the Study, the sponsor, will be notified according to the procedures for SAE reporting as outlined

in Section 6.4.3. Follow-up information regarding the outcome of the pregnancy and any fetal or neonatal sequelae will be obtained and documented.

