7.3. Assessment of Adverse Events

All AEs will be assessed by the investigator and recorded in the case report form, including the dates of onset and resolution, severity, relationship to Study drug, outcome, and action taken with Study medication.

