3.7.2. Adverse Events

Adverse events (AEs) will be coded to the preferred terms (PT) of the Medical Dictionary for Regulatory Activities (MedDRA®). Summaries for induction period and for the complete study period will be presented separately and by system organ class (SOC), preferred term, and severity and/or relatedness, the number and percentage of subjects for whom events were reported.

Adverse events (AEs) are recorded from signing of the informed consent form through the final follow-up assessment. Adverse events observed prior to first dose are non-treatment emergent.

Treatment emergent adverse events are defined as follows for induction period and overall:

- TEAEs are AEs with onset on or after the first initiation of study drug up to the date of last dose of study drug + 28 days.

Only treatment-emergent AEs will be summarized in the tables.

An AE will be considered a treatment-emergent serious AE (TESAE) if it is a TEAE that additionally meets any SAE criteria.

If more than 1 AE is coded to the same preferred term for the same subject, the subject will be counted only once for that preferred term using the most severe and most related occurrence for the summarizations by severity and by relationship to study drug.

Summary tables will also be provided for Induction period and overall for subjects with:

- TESAEs by SOC and PT
- TEAEs leading to discontinuation of study drug by SOC and PT
- Drug related TEAEs by SOC and PT
- TEAEs by severity and by SOC and PT
- TEAEs resulting in death by PT

Listings of all AEs, SAEs, and AEs leading to discontinuation by subject will be presented.

An overall summary of adverse events will also be presented and will include the following summary lines: Any AE, Moderate or Severe AEs, AEs Related to Study Drug, Moderate or Severe AEs Related to Study Drug, Serious AEs, Serious AEs Related to Study Drug, AEs Leading to Premature Study Drug Discontinuation, AEs Leading to Temporary Interruption of Study Drug, and Deaths During Study.

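### TEAEs are defined by onset date alone, while protocol 6.4.1.3 also counts worsening on study drug; unless worsening gets its own AE record, such events miss the TEAE tables

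*Protocol*

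**What the plan says.** Two parts of the protocol define what is treatment-emergent, and they differ.

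- **Protocol 8.8.2** (the analysis definition): a TEAE "will be defined as any AE that begins on or after the date of the first dose of study drug". There is no clause for worsening. Every incidence summary listed there is of TEAEs or serious TEAEs (TESAEs).
- **Protocol 6.4.1.3** (the recording rule) first says what is to be entered: "Medical events or conditions that arise or worsen in severity or frequency following informed consent will be recorded as an AE". On timing, the same sentence then says of such events: "those after initiation of Study drug will be recorded as a treatment-emergent AE". Read together, an event that worsens after study drug starts is treatment-emergent.
- **Protocol 7.1.1** (what counts as an AE) includes "Preexisting events that increase in frequency, severity or change in nature or seriousness during or as a consequence of participation in clinical studies". This defines an AE, not a TEAE, but it is where seriousness enters.

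Both SAPs adopt the narrower rule.

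- **Phase 2b SAP 3.7.2**: TEAEs are "AEs with onset on or after the first initiation of study drug up to the date of last dose of study drug" plus 28 days, and "Adverse events observed prior to first dose are non-treatment emergent". AE tables are restricted to TEAEs, and an AE is a TESAE only "if it is a TEAE that additionally meets any SAE criteria".
- **Maintenance SAP 3.7.2**: onset only, with a different end of window, the same restriction of tables to TEAEs and the same dependence of TESAE on TEAE.

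On the record itself, protocol 7.3 lists what the investigator enters, "including the dates of onset and resolution, severity, relationship to Study drug, outcome, and action taken with Study medication". Neither 7.3 nor 7.4.2 says what to do when an AE already on file gets worse.

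**The concern.** AEs are collected from consent, so some will be open at first dose. If one of these becomes more severe, becomes serious or leads to stopping on study drug, a safety table ought to count it. Under the definition used for the tables, it may not.

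The rows that could be affected include the ones read first: TESAEs and TEAEs leading to discontinuation. The two parts of the SAP could also disagree about the same subject. Phase 2b SAP 3.3.4.1 treats stopping for an AE of worsening UC as an intercurrent event, with no condition on when that AE began. The same AE, if opened during screening and kept on one record, would be absent from the TEAE discontinuation table.

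Listings show that an event happened, but they do not give incidence by arm. An undercount in the tables is therefore not repaired by a listing.

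**Working it through.** The plan gives no figure to reproduce. The check sets the rules side by side and follows one event through them.

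| Source | Onset on or after first dose | Earlier onset, worse on drug |
|---|---|---|
| Protocol 6.4.1.3 | treatment-emergent | treatment-emergent (severity or frequency) |
| Protocol 7.1.1 | AE | AE (frequency, severity, nature or seriousness) |
| Protocol 8.8.2 | TEAE | no provision |
| Phase 2b SAP 3.7.2 | TEAE | no provision; pre-dose AEs declared non-emergent |
| Maintenance SAP 3.7.2 | TEAE | no provision |

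**Step 1. Which events are exposed.** Conditions dating from before consent are medical history (protocol 7.1.1). Their first worsening after dosing creates the AE, with a post-dose onset, so they are counted. The exposed events are AEs that start between consent and first dose, are still open at first dose, and then worsen. Screening lies within 28 days of dosing (protocol 6.1), so the window is normally no longer than that.

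**Step 2. Follow such an event under the two possible recording practices.**

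- *One record, original onset kept.* The onset is before first dose, so the event fails 8.8.2 and both SAPs. It cannot be a TESAE, because that requires a TEAE. It is absent from the TEAE and TESAE tables and from the table of TEAEs leading to discontinuation, however much it worsens.
- *New record dated at the worsening.* The onset is after first dose, so the event is a TEAE and is tabulated.

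**Step 3. Which practice do the documents require?** Neither. Section 6.4.1.3 can be read as calling for a new record, but does not say so. Sections 7.1.1, 7.3 and 7.4.2 contain no instruction to close and reopen an AE.

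**Step 4. Where the event still appears under the first practice.**

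- Listings: SAEs, AEs leading to discontinuation or interruption, and AESIs (protocol 8.8.2); all AEs, SAEs and discontinuations (Phase 2b SAP 3.7.2); TEAEs and non-TEAEs (Maintenance SAP 3.7.2).
- Summaries of reasons for stopping treatment: protocol 8.8.1 and section 3.2.1 of both SAPs. These are by arm but not by preferred term.
- Dose selection: protocol 8.11 gives the committee unblinded listings of SAEs, AEs leading to discontinuation and markedly abnormal laboratory values. None is described as limited to TEAEs.

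**Step 5. Size.** The documents give neither the share of subjects with an AE open at first dose nor the share of those that worsen. For scale only, assume 10% to 20% for each, among the 240 Phase 2b subjects:

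- low: 240 × 0.10 × 0.10 = 2.4 subjects (1.0%)
- high: 240 × 0.20 × 0.20 = 9.6 subjects (4.0%)

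Both inputs are assumptions. The result covers worsening of any kind, not serious worsening, and assumes that no site opens a new record. One missed subject in an arm of 60 changes that arm's rate by 1/60 = 1.7 percentage points.

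**The case against.** The strongest reply is that 6.4.1.3 is itself a recording instruction. Worsening is to be recorded as an AE, and after study drug starts as a treatment-emergent one. On that reading the worsening is its own AE, begins after first dose, meets 8.8.2, and the sections agree. This is a fair reading, and it is why the loss is conditional. It does not settle the matter: no section states the new-record rule, and the Phase 2b SAP's sentence on pre-dose AEs has no exception for later worsening. As written, tabulation depends on site practice.

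Four stronger readings are tempting, and the documents do not support them.

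- *That these events drop out of every AE and SAE table.* This follows only under single-record practice. Even then, the summaries of reasons for stopping treatment still count a stop caused by an AE.
- *That dose selection would not see them.* Protocol 8.11 puts SAE and discontinuation listings before the committee. What it could lack is the event in the incidence tables.
- *That 6.4.1.3 itself covers an event becoming serious.* It names severity and frequency only; seriousness comes from 7.1.1.
- *That the omission biases the comparison of arms in a known direction.* Counts can only fall, but which arm loses more depends on where worsening occurs, and the documents do not show that.

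The obvious clinical examples are also weaker than they look. Worsening anaemia would show in the haemoglobin summaries and toxicity grades (Phase 2b SAP 3.7.3.1), which do not depend on AE onset. Clinically significant infection, or infection needing oral antimicrobials, within 2 weeks before Day 1 is excluded by criteria 16a and 16c. For Maintenance, the study ended early and the report is abbreviated (Maintenance SAP section 1), so the practical effect there is smaller.

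**Conclusion.** The inconsistency is real. The definition that drives the tables omits the worsening clause of protocol 6.4.1.3, neither SAP restores it, and the Phase 2b SAP reinforces the omission. If worsening stays on the original record, an AE that began between consent and first dose and worsens or becomes serious on drug is missing from the TEAE and TESAE incidence tables and from the table of TEAEs leading to discontinuation. It is not lost from the listings or from the reasons for stopping treatment.

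The number affected cannot be derived from the documents. It is probably small, because the event must start in a short window, still be open at first dose, and then worsen. The conclusion rests on one open point, how sites record worsening. The change is worth making because it is cheap and because serious and treatment-stopping events at 60 per arm are counts in which a single subject is visible.

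**What to change.** 1. In protocol 8.8.2 and section 3.7.2 of both SAPs, define a TEAE as an AE that starts on or after first dose, or that started earlier and worsens in severity or frequency, or becomes serious, on or after first dose, within the same window. In Maintenance, apply this relative to the first Maintenance dose, in line with the Day 1 definition in protocol 8.1.
2. In Phase 2b SAP 3.7.2, remove the sentence that pre-dose AEs are non-treatment-emergent, or limit it to those that do not later worsen or become serious.
3. In the CRF guidance, state that such a worsening is entered as a new AE record dated at the worsening. This step is needed as well as the definition, because the fields named in protocol 7.3 include no date of worsening.

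The cost is one sentence in each document and a CRF completion note. TEAE counts rise slightly and a few AE records are split. Splitting does not double-count subjects within a preferred term, since both SAPs already count a subject once per term at the greatest severity.
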